9.4 Statistical Analyses

9.4.1 General Approach

After examining for outliers and missing values, the distributions of continuous measures will be examined. When necessary, the data may be transformed or non-parametric tests will be used. Baseline measures will be compared between the treatment groups to identify imbalances. All statistical analyses will be performed using SAS 9.4 (SAS Institute Inc., Cary, NC) with two-sided 5% level of significance.

Implementation of the planned statistical analysis will be described in the Statistical Analysis Plan (SAP) prior to locking the database.

9.4.2 Analysis of the Primary Efficacy Endpoint(s)

Anatomical Surgical Outcome

The primary endpoint for the surgical treatment is dichotomous: success or failure at 24 months after surgery. The primary outcome measure uses the rectal compression ratio at 24 months unless there has been retreatment at an earlier time. When there is retreatment, or when the 24-month ultrasound results and POPQ results are missing and the last observed measurements were consistent with the definition of failure, then the results at 24 months will be imputed to be a failure. A sensitivity analysis will be performed to study the effect on the primary endpoint of different methods of handling dropouts and missing data. It will be conducted by assuming various values for the imputed outcomes and comparing the results under those assumptions to the results of the primary analysis.

Cochran-Mantel-Haenszel (CMH) test will be used to compare between surgical treatments adjusting for stratification factor. In addition, Generalized linear mixed-effects models (GLMMs) will be performed to yield an effect estimate of conditional on surgeon. Demographics and other characteristics at baseline (treatment group, age, BMI, menopausal status, parity, duration and severity of ODS) will be included. Surgeon will be included as a random effect to account for

correlation between outcomes of patients treated by the same surgeon. Adjusted odds ratios (ORs) will be presented with 95% confidence intervals (CIs).

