2.3.3. Assessment of Potential Risks and Benefits

We believe that the risks and benefits to the participants are balanced in this study design. Exam, questionnaires, and imaging used in the study are minimally invasive and part of routine urogynecology care. While standard risks of surgery apply to the surgical procedures, previous studies have demonstrated the safety of the two procedures. If participants in either treatment group develop new symptoms after surgery, treatment is available. Currently, patients with ODS receive treatment without follow-up that would allow sufficient assessment of the safety and efficacy of the surgical outcome, which could otherwise guide more effective clinical decisions.

3. Outcomes and Measurements

Primary Outcome: Compare surgical success or failure in female participants with moderate to severe OD symptoms, and rectal hypermobility diagnosed by ultrasound, who are randomized to minimally invasive transvaginal sacrospinous rectopexy versus laparoscopic abdominal ventral rectopexy at 24 months after surgery. The primary outcomes will be measured by:

1. The degree of rectal hypermobility measured via ultrasound (i.e. compression ratio).
 - a. "Compression ratio" will be calculated as a means to quantify the relative change in length of the rectovaginal septum (RVS), in other words the degree of hypermobility / sliding rectum, and is expressed as a percentage using the following formula: $CR = (RVS_r - RVS_v) / RVS_r * 100$, where RVS_r (Rectovaginal Septum) and RVS_v represent the RVS length at rest and Valsalva.

The criteria for surgical failure will be defined as follows:

1. A participant will be considered a surgical failure if:
 - a. Rectal hypermobility with compression ratio more than 20% is detected via ultrasound.
2. Otherwise, a participant will be considered a surgical "success".

Secondary Outcome:

- Compare efficacy and safety of the surgery measured by:
 1. Postoperative pain - Participants will complete the Pain Scale (67) and an assessment of pain medication use preoperatively, and then at 2 weeks and 2, 12, and 24 months postoperatively.
 2. Postoperative functional activity level – Participants will complete the Activity Assessment Scale (68) which measures functional activity preoperatively and then at 2 weeks and 2, 12, and 24 months postoperatively.

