9.2 Sample Size Determination

Based on our preliminary studies in literature (83-87), we assume an anatomic success rate in LAVR group is about 70% at 24 months. The investigators believe that a difference in success rates less than 25% will not change clinical practice, but also that the sample size should be large enough so that an observed difference in success rates of 20% would be significant; i.e., an inability to differentiate between the procedures will require an observed difference that is less than 20%.

The study will be individually randomized group-treatment trial (IRGT), which patients are randomized to surgical interventions through a common surgeon (88-90). There will be three surgeons performing each surgical treatment. The number of surgeons and patients will be the same in each clinical site. We anticipate an average of 16 individually randomized patients per surgeon in each treatment group. Outcomes for patients treated by the same surgeon tend to be more similar. We assume minimal variability, estimating a small intraclass correlation coefficient (ICC) of 0.01. The table below illustrates power to detect at least 23% difference between treatment groups with varying assumptions on ICC and dropout rates. A total of 96 patients (48 patients per group) would yield 86% power to differentiate between anatomical success rates of 70% and 93% assuming an ICC of 0.01 and a two-sided 5% level of significance. Projecting a 20% dropout/loss to follow up rate over 2 years, we anticipate recruiting and up to 120 total patients.

ICC	% Dropout	Total patients	Average patients per surgeon	Power
0.01	0	120	20	92%
	10	108	18	90%
	20	96	16	86%
0.02	0	120	20	90%
	10	108	18	87%
	20	96	16	83%
0.05	0	120	20	82%
	10	108	18	79%
	20	96	16	76%

Due to concerns that ICC is higher than expected or dropout rate is higher than 20% toward the end of 2-year follow-up, we calculated the sample size that would be needed for 87% power to differentiate between anatomical success rates of 70% and 95% (a difference of 25%) in treatment groups with a two-sided 5% level of significance. The required sample size is 39 per group, or 78 total patients.

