9.3 Populations for Analyses

Modified Intent-to-treat (mITT) Population

The mITT population will include all randomized participants who received at least one post-op visit. Participants will be analyzed according to their randomized treatment assignment, regardless of the treatment actually received.

Safety Population

The safety population will include all participants who received any study treatment. All safety analyses will use the safety population. Participants will be analyzed according to the treatment they actually received, regardless of the treatment assigned.

Per-protocol (PP) Population

The PP population is a subset of the ITT population who completed the study without any major protocol violations. Analyses will exclude the following randomized participants: (83) those who did not receive TSR/LAVR surgery as planned; (84) those who died within 12 months of surgery and were not assessed on the primary outcome before their death; (85) those who withdrew from study and withdrew consent for use of their data.

Full Analysis Set (FAS)

The FAS will include all randomized participants who receive any study treatment and have at least one assessment since the baseline visit. Participants will be analyzed in their randomized treatment assignment, regardless of the treatment actually received.

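### The primary missing-data rule can only impute failure, gives no value to dropouts last seen as successes, and names no analysis population

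*Combined protocol and SAP*

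**What the plan says.** Section 9.4.2 makes the primary endpoint success or failure at 24 months, based on the ultrasound compression ratio. Two events are set to failure. One is earlier retreatment. The other arises "when the 24-month ultrasound results and POPQ results are missing and the last observed measurements were consistent with the definition of failure". The section imputes a success nowhere and names no analysis population.

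It adds a sensitivity analysis "to study the effect on the primary endpoint of different methods of handling dropouts and missing data". On method it says: "It will be conducted by assuming various values for the imputed outcomes", then "comparing the results under those assumptions to the results of the primary analysis". It lists no scenarios.

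Other sections touch the same patients:

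- Sections 3 and 8.1 define failure as a ratio above 20%, with no mention of POPQ, and continue: "Otherwise, a participant will be considered a surgical" success.
- Section 9.2: "A total of 96 patients (48 patients per group) would yield 86% power", followed by "Projecting a 20% dropout/loss to follow up rate over 2 years" to reach 120 recruited.
- Section 9.3: "The mITT population will include all randomized participants who received at least one post-op visit". A full analysis set with a similar entry condition is also defined. Neither requires a 24-month result.
- Section 9.4.1 leaves implementation to a SAP due before database lock.

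**The concern.** The rule treats two kinds of dropout differently. One whose last ratio was above 20% stays in the analysis as a failure. One whose last ratio was 20% or below has no stated outcome. A participant with a 24-month POPQ but no 24-month ultrasound also has none, even if her last ratio was failing, because both measurements must be missing before the rule applies. That last group should be small, since the two assessments share visits in the Schedule of Activities.

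If patients without a value drop out of the denominator, the retained dropouts are all failures. Each arm's success rate is then too low even when dropouts resemble completers. The arm with more failing dropouts loses more, so the difference between arms moves as well. If the same patients are counted as successes, the estimate is different. The choice could be settled as late as just before database lock, in a trial where section 6.3 says surgeons and participants cannot be masked.

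**Working it through.** **Inputs from the plan (section 9.2).** Success 70% (LAVR) and 93% (TSR); 96 evaluable; 20% dropout. Check of the recruitment figure: 96 / 0.80 = 120, as stated. So 24 dropouts are projected, 12 per arm if equal, with 48 completers per arm.

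**Input the plan does not give.** The share *f* of dropouts whose last observation was a failure. The main case assumes the design failure rates, 30% and 7%. Dropouts are assumed not to have been retreated.

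**How many get a value.** Set to failure: 12 × 0.30 + 12 × 0.07 = 3.6 + 0.84 = 4.4. No stated value: 24 − 4.4 = 19.6.

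**Reading 1: those without a value are excluded.** Success = completers' successes / (completers + dropouts set to failure).

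- LAVR: 48 × 0.70 / (48 + 3.6) = 33.6 / 51.6 = 65.1%
- TSR: 48 × 0.93 / (48 + 0.84) = 44.64 / 48.84 = 91.4%
- Difference: 26.3 points. About 100.4 patients are analysed, not the 96 of section 9.2.

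**Reading 2: those without a value count as success.**

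- LAVR: (33.6 + 12 × 0.70) / 60 = 70.0%
- TSR: (44.64 + 12 × 0.93) / 60 = 93.0%
- Difference: 23.0 points.

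**Other values of *f*.** The third row uses the pilot TSR ratio at 2 months in section 4.2 (mean 9.2, SD 13.7, 20 patients) with a normal approximation: 1 − Φ((20 − 9.2)/13.7) = 21.5%.

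| *f*, LAVR/TSR (assumption) | Set to failure | No value | Difference if excluded | Difference if success | Gap |
|---|---|---|---|---|---|
| 30% / 7% | 4.4 | 19.6 | 26.3 | 23.0 | 3.3 |
| 15% / 3.5% | 2.2 | 21.8 | 24.7 | 20.7 | 4.0 |
| 30% / 21.5% | 6.2 | 17.8 | 23.1 | 20.1 | 3.0 |

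The count is sensitive to *f*. The pilot's 12-month ratio (mean 19.6, SD 14.4) gives 1 − Φ((20 − 19.6)/14.4) = 48.9%; applied to both arms, it leaves 24 − 24 × 0.489 = 12.3 without a value.

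**No true difference (70% in both arms), reading 1, *f* = 30%.** Success = (1 − d) × 0.70 / [(1 − d) + d × 0.30], where d is dropout.

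- Equal dropout: both arms move equally, so the gap is 0.
- LAVR 25%, TSR 15% (assumption): 0.525 / 0.825 = 63.6% vs 0.595 / 0.895 = 66.5%, a spurious 2.8 points in favour of the arm with less dropout.

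Type I error was simulated with 200,000 trials per setting, two sites with 30 per arm each, a site-stratified CMH test without continuity correction, and no surgeon clustering. It was 4.9% to 5.0% at equal dropout. At 25%/15% dropout it was about 5.3% (*f* = 15%) to 6.0% (*f* = 30%).

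**Screening ratio.** Inclusion requires a ratio above 50%, and the 2-week visit has no ultrasound. Read literally, anyone lost before month 2 was last observed as a failure. If 2% to 5% of each arm (assumption) lack a post-operative ultrasound, 23.0 × 0.98 = 22.5 and 23.0 × 0.95 = 21.9 points. This needs only a clarification.

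**The case against.** The best defence reads section 9.4.2 together with sections 3 and 8.1. The endpoint has two values, the failures are listed, and everyone else is a success. That amounts to carrying the last observation forward, and at the design rates it returns exactly 70% vs 93%. On this view the 96 in section 9.2 is only a recruitment allowance.

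The reading is possible but is not what the plan states. Sections 3 and 8.1 define the outcome of a measured ratio; they are not a missing-data rule, and section 9.4.2 does not invoke them. Applied literally, the default would also score as a success a participant whose last ratio was failing and who has a 24-month POPQ but no ultrasound.

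The second defence is that a sensitivity analysis and a later SAP are planned. A reader might infer that the plan has no answer for these dropouts at all. That goes too far: the stated purpose of the sensitivity analysis covers all dropouts and missing data. But its method sentence varies only imputed outcomes, and its comparator is a primary analysis that is undefined for these patients. It cannot supply the primary value.

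The third defence is that the effect is small, and much of this stands. The 3 to 4 point gap is about half a standard error: √[(0.70 × 0.30 + 0.93 × 0.07)/48] = 7.6 points. Unclustered power hardly differs between the readings: 92.4% vs 92.5%, 89.6% vs 88.7% and 82.1% vs 81.2% for the three rows of the table (excluded vs counted as success).

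**Conclusion.** The concern holds. As written, the rule assigns missing outcomes in one direction only and leaves the remaining dropouts, and the population, unstated. If those dropouts are excluded, success rates are biased downward in both arms, and the planned difference becomes 26.3 instead of 23.0 points. This assumes 20% dropout in each arm, dropouts last seen failing at the design rates, and no retreatment among them. About 20 of 24 without a value is likewise conditional on that assumption and is not a figure from the plan.

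A reader might infer that the rule builds in a false advantage for TSR. The documents do not support that. They do not say that these dropouts are excluded. Even under exclusion, equal dropout with no true difference gives no bias, and they project no difference in dropout between arms. A spurious gap needs unequal dropout, favours whichever arm loses fewer patients, and is modest at 25%/15%. The point should be fixed, but it does not invalidate the design.

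**What to change.** In section 9.4.2 and the SAP, settle these points before outcomes accumulate:

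1. State one symmetric rule for every missing 24-month ultrasound other than after retreatment, whatever the last value was. One option is multiple imputation of the compression ratio from baseline, 2- and 12-month ratios, arm and site, followed by the 20% cut-off. A simpler one is to carry forward the last post-operative ratio, whether success or failure, with a stated rule for participants who have none.
2. Name the population for the primary analysis.
3. Delete the POPQ condition.
4. State that the screening ratio is not a last-observed outcome.
5. Have the sensitivity analysis vary all missing outcomes separately by arm, for example as a tipping-point analysis.

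The cost is wording and modest extra analysis; the ultrasounds needed are already scheduled. Multiple imputation relies on a missing-at-random assumption, which the tipping-point analysis would test. Carrying forward assumes no change after the last visit, which is doubtful because the pilot mean ratio rose from 9.2% at 2 months to 19.6% at 12 months (section 4.2).

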6.3 Measures to Minimize Bias: Randomization and Blinding

Randomization

Participants will be assigned with equal probability to one of the two groups for each intervention TSR with and without CVPR versus LAVR with and without CVPR. Participants will be randomized after anesthesiologist clearance for both surgical approaches and prior to the preoperative visit. Every effort will be made to minimize the time between randomization and the surgery. Participant will have the opportunity to review the surgery detail with the surgeon during the preoperative visit. Separate randomization schedules will be generated by the DCC for each Clinical Site using a random permuted block design. The DCC will provide treatment allocations to the Clinical Sites using REDCap randomization feature.

Masking

The study surgeon is providing clinical care to enrolled participants, thus masking the surgeon to treatment allocation or participant symptoms is not practical or feasible, other than the allocation concealment prior to surgical randomization. Given the surgical procedure require a transvaginal or abdominal incision, it is clinically not possible to mask the participant or other research personnel. Every attempt will be made to keep the research coordinator blinded when assessing symptoms via questionnaires during follow up visits. The dynamic pelvic ultrasound image will be saved and re-evaluated in a blinded manner retrospectively to confirm the results of the initial reading.

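### The CMH comparison of arms on the primary endpoint has no surgeon term, and the plan does not say whether it or the surgeon random-effect model decides the trial

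*Combined protocol and SAP*

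**What the plan says.** Section 9.4.2 gives two analyses of the dichotomous 24-month outcome. The first: "Cochran-Mantel-Haenszel (CMH) test will be used to compare between surgical treatments adjusting for stratification factor". The second: "In addition, Generalized linear mixed-effects models (GLMMs) will be performed to yield an effect estimate of conditional on surgeon". The second model has surgeon as a random effect and a list of baseline covariates, and it yields adjusted odds ratios with 95% intervals. Site is not in that covariate list. The same section compares its sensitivity analyses with a primary analysis but does not say which of the two that is.

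Section 9.4.1 sets the level: "All statistical analyses will be performed using SAS 9.4 (SAS Institute Inc., Cary, NC) with two-sided 5% level of significance".

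Section 9.2 describes an individually randomized group-treatment trial and says "Outcomes for patients treated by the same surgeon tend to be more similar". On numbers: "There will be three surgeons performing each surgical treatment. The number of surgeons and patients will be the same in each clinical site", and "We anticipate an average of 16 individually randomized patients per surgeon in each treatment group". The planning ICC is 0.01, and the power table also shows 0.02 and 0.05. On power: "A total of 96 patients (48 patients per group) would yield 86% power to differentiate between anatomical success rates of 70% and 93" per cent, at ICC 0.01.

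Section 6.3 says "Participants will be assigned with equal probability to one of the two groups for each intervention", with a separate randomization schedule for each site. Section 6.2.1 gives the transvaginal operation to urogynecologists and the laparoscopic one to colorectal surgeons.

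**The concern.** The design recognises that patients of one surgeon are correlated, but the test written as the comparison of arms treats them as independent. Stratifying CMH by surgeon cannot repair this. Each surgeon operates in one arm only, so a surgeon stratum holds no comparison.

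If CMH is the test relied on, the superiority claim of section 9.1 is not tested at the stated 5%. A difference between two sets of three surgeons could be read as a difference between operations. If the mixed model is the test relied on, the plan gives no df method for a model with six surgeons. If the two disagree, the plan does not say which governs.

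**Working it through.** **Inputs.** Two-sided 5% (9.4.1); 1:1 allocation within site (6.3); three surgeons per arm, 16 patients per surgeon on average, 48 per arm, ICC 0.01/0.02/0.05, success 70% vs 93% (9.2); surgeons nested in arm (6.2.1).

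**Surgeon loads.** 96/16 = 6 surgeons in all. Equal numbers of surgeons at two sites means three per site, so each arm has two surgeons at one site and one at the other. Two cases were taken: 16/16/16 per arm, and 12/12/24. The second follows from 24 patients per arm per site if each surgeon works at one site, which is an assumption.

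**1. The plan's power figure.** Unpooled formula without clustering: SE = √((0.70×0.30 + 0.93×0.07)/48) = √(0.2751/48) = 0.0757. Then 0.23/0.0757 − 1.96 = 1.08, so power is 86.0%. With 54 and 60 per arm the same formula gives 89.7% and 92.5%. The table's ICC 0.01 rows are 86, 90 and 92%.

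Now apply the design effect at ICC 0.01: DE = 1 + 15×0.01 = 1.15, and effective n = 48/1.15 = 41.7. Power is 80.9% unpooled, 78.3% pooled and 81.3% by arcsine. The stated 86% is therefore not reproduced from its own ICC.

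**2. Size of the CMH test.** DE = 1 + (Σm²/Σm − 1)×ICC, and size = 2[1 − Φ(1.96/√DE)]. For 16/16/16, Σm²/Σm = 16. For 12/12/24 it is (144 + 144 + 576)/48 = 18.

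| ICC | DE, 16 each | Size | DE, 12/12/24 | Size |
|---|---|---|---|---|
| 0.01 | 1.15 | 6.8% | 1.17 | 7.0% |
| 0.02 | 1.30 | 8.6% | 1.34 | 9.0% |
| 0.05 | 1.75 | 13.8% | 1.85 | 15.0% |

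The site-stratified CMH test was also simulated under the null with beta-binomial surgeon effects, 200,000 trials per setting. Size was about 4.9% at ICC 0, 6.7–7.0% at 0.01, 8.6–9.0% at 0.02 and 14–15% at 0.05. Because size is correct at ICC 0, the excess comes from clustering.

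**3. Power of a test on surgeon-level data.** The six surgeon proportions were regressed on treatment, weighted by patients, for 70% vs 93%:

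| ICC | 16 each, 3 df (site in) | 16 each, 4 df (no site) | 12/12/24, 3 df | 12/12/24, 4 df |
|---|---|---|---|---|
| 0.01 | 47% | 56% | 50% | 58% |
| 0.02 | 43% | 52% | 47% | 53% |
| 0.05 | 35% | 42% | 39% | 44% |

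The size of this test with 12/12/24 loads was 5.1–5.7% across these ICCs. At ICC 0 the 3-df version already has only 51–54% power, so most of the loss is due to the few df.

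**4. Interval width.** At ICC 0.01 the median 3-df 95% half-width is about 23 points. Treating patients as independent gives 1.96 × 0.0757 = 14.8 points.

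**The case against.** The strongest reply is that the plan does model surgeon. Section 9.4.2 includes the random effect expressly for within-surgeon correlation, and section 9.4.3 refers back to mixed models as the method described for the primary endpoint. This stands in part. A reader might infer that the plan ignores clustering, or that CMH is the declared deciding test. The documents support neither. CMH is the implied test, because it is the one said to compare the arms while the mixed model is added for estimation. The later SAP mentioned in section 9.4.1 covers implementation and does not itself settle the choice.

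A second reply is that the inflation presumes surgeons sampled from a wider population. If the question is the effect in the hands of these six surgeons, this inflation does not arise. That is correct, and it is an assumption of this point. The group-treatment design, the ICC and the random surgeon effect all take the wider view.

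Third, the ICC is unknown. The documents give no evidence on it for this outcome, so 14–15% should not be read as the trial's expected error rate. At the planning value the excess is about 2 points.

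Fourth, the 12/12/24 loads are constructed. They change little, since equal loads give nearly the same size. If section 9.2 meant three surgeons per arm at each site, there would be 8 patients per surgeon and sizes of 5.8% and 9.2% at ICC 0.01 and 0.05. That reading conflicts with the 16 per surgeon in the plan's own table.

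**Conclusion.** The point holds in a limited form. The test written as the comparison of arms does not hold the stated two-sided 5% level under the plan's own clustering assumptions, and the deciding analysis is not named. True size is about 6.7–7.0% at ICC 0.01, 8.5–9.0% at 0.02 and, as a stress case, 14–15% at 0.05. This assumes 96 patients analysed, three surgeons per arm, surgeons viewed as a random sample, and an ICC that also applies under the null.

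A reader might set about 50% power against the stated 86% and call the gap the cost of clustering. The figures do not support that. Most of the gap comes from estimating variance on 3 df, and part from a stated 86% that matches a calculation with no clustering. Nor does that match show that clustering was left out of the whole table, because its power falls as the ICC rises. The documents do not give the formula used.

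**What to change.** In section 9.4.2, name one surgeon-accounting analysis as the single primary test, before database lock.

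- The smallest change is to make the planned surgeon random-effect model primary, add site to it, and state a small-sample df method in advance (about 3–4 df with six surgeons).
- A patient-weighted regression of the six surgeon proportions on treatment and site, on 3 df, is an acceptable alternative. Leaving site out gives 4 df and must also be fixed in advance.
- Take the primary p-value and confidence interval from the same analysis. Keep CMH as supportive.
- In section 9.2, state how the surgeons of each arm are spread over the two sites, and restate power for the chosen test.

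The change is to wording and needs no new data. It brings wider intervals (about 23 against 15 points at ICC 0.01 for the 3-df analysis) and a much lower stated power. For a surgeon-level t test this is about 47–58% at ICC 0.01. The mixed model's power depends on the df method and should be simulated. If the team finds that power too low, it could consider more surgeons: the same 48 patients per arm spread over six surgeons with 8 each gives about 75% with site in the model (9 df) at ICC 0.01. That is a design option and not part of this fix.

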9.4.4 Safety Analysis

Any endpoints that relate to safety will be analyzed using methods previously described.

All adverse events collected will be coded. Events will be summarized cumulatively through the following time points: 2 weeks, 2 months, 12 months, and 24 months postoperatively. Severity and frequency of AEs will be presented. In addition, the frequency and percentage of participants who had a Serious AE (SAE) or a related AE will be tabulated separately.

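### The only stated primary effect estimate is an adjusted odds ratio from a seven-term mixed model that, at the planned rates, would rest on about 18 failures; a penalised fit and a risk difference should be prespecified.

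*Combined protocol and SAP*

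**What the plan says.** Section 9.4.2 defines the primary endpoint as success or failure at 24 months. It gives two analyses. The CMH test, adjusted for the stratification factor, compares the arms. In addition, a mixed model supplies an effect estimate conditional on surgeon, reported as adjusted ORs with 95% CIs. On its fixed part the section says: "Demographics and other characteristics at baseline (treatment group, age, BMI, menopausal status, parity, duration and severity of ODS) will be included". That is treatment plus six covariates; surgeon is a random effect.

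The section names no common OR from the CMH analysis, no risk difference and no unadjusted estimate. It names no estimation method for the mixed model and no rule for an arm without failures. Its one sensitivity analysis concerns dropouts and missing data. Section 9.4.1 leaves implementation to an SAP to be written before database lock.

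Section 9.2 sizes the trial on 48 evaluable patients per group and "anatomical success rates of 70% and 93% assuming an ICC of 0.01". On recruitment it says: "Projecting a 20% dropout/loss to follow up rate over 2 years, we anticipate recruiting and up to 120 total patients". On surgeons it says: "There will be three surgeons performing each surgical treatment".

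**The concern.** The information in a logistic model is limited by the rarer outcome, here failure. If TSR works as well as the sizing assumes, there will be few failures, and very few in the TSR arm. Ordinary maximum likelihood then pushes the OR away from 1, and it has no finite solution when one arm has no failures. Because the adjusted OR is the only effect measure named, the headline size of benefit would tend to be too large in the scenario the sponsor expects, and in a few trials it could not be reported as planned. A remedy chosen after seeing sparse data would be post hoc.

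**Working it through.** **The plan's own figures.** 96/0.80 = 120 recruited, which reproduces. The stated 86% power follows from 48 per group, 70% v 93%, two-sided 5%, unpooled normal approximation, with no allowance for clustering (85.95%). With the stated ICC of 0.01 and 16 patients per surgeon, the design effect is 1 + 15 × 0.01 = 1.15 and power is 80.9%. That mismatch is a separate matter and does not affect this point. The plan states no event count.

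**Expected failures (Section 9.2 rates).**
- 48 per arm: 48 × 0.30 + 48 × 0.07 = 14.4 + 3.4 = 17.8, or 17.8/7 = 2.5 per fixed effect.
- 60 per arm, nobody lost: 60 × 0.37 = 22.2, or 3.2 per fixed effect.

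**True OR for success, TSR v LAVR.** (0.93/0.07)/(0.70/0.30) = 5.69.

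**Chance of no TSR failure.** 0.93^48 = 3.1%; 0.93^60 = 1.3%.

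**Simulation of the planned model.** Six surgeons nested in arm, ICC 0.01, treatment plus six non-prognostic covariates (one degree of freedom each), random-intercept logistic model fitted by maximum likelihood, 48 per arm, 70% v 93%, runs of 1,500 and 2,500 trials:

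| Quantity | Result |
|---|---|
| Median OR, finite fits | 6.68 and 6.91 (17% and 21% above 5.69) |
| Geometric mean OR, finite fits | 7.15 and 7.39 |
| Finite-fit ORs above twice the true value (1,500-trial run) | about 29% |
| No finite OR | 3.5% and 2.9% |
| Geometric mean of the unadjusted OR, finite fits | 6.04 |

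In the 2,500-trial run, 2.84 of the 2.88 percentage points without a finite OR were trials with an arm that had no failures. The two problems therefore have different causes: the covariate load drives most of the inflation, and the empty cell drives the missing estimates.

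**Dependence on the TSR success rate** (LAVR 70%, 48 per arm, same seven terms):

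| TSR success | Expected failures | True OR | Median fitted OR |
|---|---|---|---|
| 93% | 17.8 | 5.69 | 6.7 to 6.9 |
| 85% | 21.6 | 2.43 | 2.66 in one run, about 2.8 in another |
| 80% | 24.0 | 1.71 | 1.7 to 1.8 |
| 70% | 28.8 | 1.00 | 1.00 |

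**Comparators at 70% v 93%, 48 per arm.**
- Firth-penalised logistic regression with the same seven terms (surgeon effect in the data, none in the fit): finite in all 2,500 trials, mean log-OR bias −0.005, an OR of 5.67.
- Maximum likelihood with treatment and one covariate: bias +0.11, and still not finite when an arm has no failures.
- Unstratified risk difference: always finite, mean 0.231, SD 0.077.
- Wald 95% intervals from maximum likelihood covered 96% to 97% of the time among finite fits (fixed-effects fit).

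**The case against.** The strongest reply is that nothing decisive rests on this model. The named comparison is the CMH test, whose p-value depends neither on the covariates nor on whether the mixed model converges. Among finite fits the interval covers as it should, and the bias of about 0.23 on the log scale is about 0.3 of the estimate's standard deviation (0.76). All of that stands.

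The size also depends on 93% success. The pilot series in Section 4.2 reports a mean compression ratio of 19.6% (SD 14.4) at 12 months, against a failure threshold of 20%. If normally distributed, about 49% of TSR patients would fail. That gives 14.4 + 48 × 0.49 = 37.9 failures, no separation, and a log-OR bias of only −0.08. Failures imputed under Section 9.4.2 would also raise the count. This stands too, although the planned estimate should work under the assumption that sized the trial.

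The deferral to a later SAP is fair, but the terms and the reported measure are already fixed here.

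Three stronger readings are tempting, and the documents do not support them:
- **That the covariates must be demoted to a sensitivity analysis.** Penalisation removes the bias with all seven terms kept, and dropping covariates does not cure the empty cell.
- **That the same model will often fail on safety endpoints.** Section 9.4.4 says "Any endpoints that relate to safety will be analyzed using methods previously described", which need not mean the seven-term model, and it separately tabulates adverse-event frequencies.
- **That 13.5% of trials (0.95^39) will lack a finite OR.** That comes from the contingency calculation of 39 per group at 70% v 95%, not from the planned size.

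**Conclusion.** The point holds as a worthwhile, inexpensive improvement, not as a flaw in the trial's main test. Under the plan's sizing assumptions, the only stated effect estimate would be about 20% too high at the median. It would not exist in about 3% of trials, or 1.3% if all 60 per arm are analysed. This rests on unpenalised maximum likelihood, one degree of freedom per covariate, non-prognostic covariates and TSR success near 93%. In a run with two prognostic covariates the geometric mean OR was 7.61.

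A reader might infer that the plan favours TSR whatever the truth, or that it raises the false-positive rate. It does neither: there is no bias when the arms are equal, and the CMH p-value is untouched.

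**What to change.** In Section 9.4.2, and in the SAP before outcome data are seen by arm:

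1. Keep the listed covariates, but fit the adjusted model with a penalised (Firth-type) likelihood and report its OR and 95% CI.
2. State how surgeon is handled in that fit. Each operation has its own surgeons (Sections 6.2.1 and 9.2), so ordinary fixed surgeon effects would be aliased with treatment. The penalised fit checked above had no surgeon term, so the chosen form should be tried on simulated data first.
3. Report a site-stratified risk difference with a 95% CI beside the CMH test. It stays finite when an arm has no failures; the interval method should be named and should suit a zero cell.

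The cost is slightly more programming and some shrinkage of the OR. No new data, visits or patients are needed.
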